### **Inclusion Criteria**

Being educated in 3rd and 4th grade

Volunteer to participate in the research

Consent of the student's parent

Speak and understand Turkish

### **Exclusion Criteria**

Being visually and hearing impaired

Using a language other than Turkish

Not willing to participate in the study

### **Research Groups**

#### **Intervention arm**

Experimental group will be selected from the branches 3rd and 4th grade. 3 branches will be selected for the experimental group. Branches will be determined by drawing. In order not to interfere with the education of students during the training, the groups will be designated as class branches. Students selected for the experimental group will be trained by the researcher for school accidents prepared in line with the components of the Health Belief Model. The training program will be planned as 30 minutes per week for 4 weeks. Before the training and at the end of the training (at the end of the 4th week), the students will be applied personal information form and a behavior scale for safety precautions in school accidents.

#### **Control Arm**

Control group will be selected from the branches 3rd and 4th grade. 3 branches for the control group. Branches will be determined by drawing. In order not to interfere with the education of students during the training, the groups will be designated as class branches. After the training of the experimental group is completed and the final data are obtained, a 40-minute training will be given to the control group about prevention from school accidents. This training was planned so that the control group would not be devoided of the intervention.

### **Data Collection Tools**

The data will be obtained with the personal information form and the behavior scale for safety measures in school accidents.

#### **Personal Information form**

In this form prepared by the researchers, there are questions that determine personal characteristics such as age, gender, educational status of parents, school accident status.

### **The Scale of Behavior of Students towards Safety Measures in School Accidents**

This scale, developed by Gür and Yıldız (2009), consists of 4 factors. Factor 1 is Unsafe Behaviors, Factor 2 is Safe Behaviors, Factor 3 is Safe Behaviors Towards Outside, and Factor 4 is Behaviors in the Service Vehicle. The questions are scored in the opposite direction. The scale consists of 40 items and is a 5-point Likert type scale. For each item, it is required to tick one of the options “Always”, “Often”, “Sometimes”, “Rarely”, “Never”. For each question, “Always” receives 5 points, “Often” receives 4 points, “Sometimes” 3 points, “Rarely” 2 points, and “Never” receives 1 point. 2nd, 3rd, 4th, 5th, 7th, 10th, 12th, 20th, 21st, 22nd, 26th, 32nd, 34th, 36th, 37th, 38th, 39th. Questions are scored in the opposite direction. The lowest score that can be obtained from the scale is 40, and the highest is 200. The highest score obtained from the scale shows that the student takes the security measures for school accidents at the highest level.

### **Ethical Considerations**

Ethical permission was obtained from the Ethics Committee of Afyonkarahisar Sağlık Bilimleri Üniversitesi (Afyonkarahisar Health Sciences University) (date: 03.June 2022; Number: 2022/340)

### **Statistical Analysis**

In the evaluation of the data, percentage, arithmetic mean, t-test for independent samples and t-test for dependent samples will be used. Significance level will be taken as  $p < 0.05$ .

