## **Hypothesis**

Education for school accidents, prepared in line with the components of the Health Belief Model, affects the safety precautionary behavior of students for school accidents.

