## **Primary Outcomes**

Behavior of Students for Safety Precautions in School Accidents

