## **Method**

### **Study Design**

This research was designed as quasi-experimental. It has a pretest-posttest design with a control group.

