### **Sample**

The behavior score averages and standard deviations of the two groups in a previous study (Dilek, 2018) and the effect size were calculated to determine the sample size of the study. Power analysis (significance level 0.05 for type 1 error, effect size 0.50, and power 0.95). (Gpower 3.1 version) was carried out. In the power analysis, the minimum number of participants was 87 in the experimental group and 87 in the control group. In this context, the research will be conducted with 100 participants in each group, taking into account the possibility that non-parametric statistics may need to be used due to the non-normal distribution of the dependent variable, incomplete and erroneous data, and absenteeism. Experimental and control groups will be selected from the branches 3rd and 4th grade. 3 branches will be selected for the experimental group and 3 branches for the control group. Branches will be determined by drawing. In order not to interfere with the education of students during the training, the groups will be designated as class branches.

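### A pre-test is planned, but no between-arm comparison adjusted for it is specified, and the score entering the independent t-test is not stated

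*Combined protocol and SAP*

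**What the plan says.** The Statistical Analysis section is the whole analysis plan. It states that "percentage, arithmetic mean, t-test for independent samples and t-test for dependent samples will be used", at a 0.05 significance level.

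The design supplies a baseline. Study Design says: "It has a pretest-posttest design with a control group". The Intervention arm section gives the timing, "Before the training and at the end of the training (at the end of the 4th week), the students will be applied" the personal information form and the behavior scale. The Control Arm section does not repeat this schedule; a control pre-test follows from the Study Design statement.

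The Primary Outcomes section gives only a construct, "Behavior of Students for Safety Precautions in School Accidents", with no time point and no choice between final score and change. The Hypothesis is that the education "affects the safety precautionary behavior of students for school accidents". The Sample section bases the effect size on "The behavior score averages and standard deviations of the two groups in a previous study", again without saying which score, and sets the allocation: "3 branches will be selected for the experimental group and 3 branches for the control group".

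**The concern.** The hypothesis concerns an effect of the education, so it needs a comparison between arms. Of the listed tests only the independent t-test provides one. The sample size basis suggests it is the main test, but the plan does not say what goes into it. The week-4 score and the change from pre-test both fit the text. They differ in precision and react in opposite ways to a baseline difference, so the choice should not be left until the data are seen.

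Neither option is a comparison adjusted for the pre-test. A week-4-only test leaves the pre-test unused. A change-score test uses it, but gives it a fixed weight of one whatever the correlation between the two measurements.

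The dependent t-tests compare each arm with itself and cannot test the hypothesis. The plan does not say it will draw conclusions from them, so this is a matter of labeling.

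At stake are mainly precision and a single estimate that is sensitive to a chance baseline gap. With three classes per arm, precision is scarce and such gaps are not rare.

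**Working it through.** **Inputs from the documents.** Effect size d = 0.50, alpha 0.05 and power 0.95; minimum 87 and planned 100 per group; three classes per arm (all from Sample). Sidedness is not stated.

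**Assumptions.** Pre/post correlation r = 0.3, 0.5, 0.7, equal at pupil and class level unless stated; equal pre and post SDs; d in week-4 SD units; intraclass correlation (ICC) 0 to 0.10. The documents give neither r nor ICC.

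**1. The plan's own figure.** By the normal formula, n = 2(z₁ + z₂)²/d². One-sided: 2(1.645 + 1.645)²/0.25 = 86.6, so 87, as stated. Two-sided: 2(1.960 + 1.645)²/0.25 = 104. The stated 87 therefore matches a one-sided, unadjusted comparison of two means. The figures below are two-sided unless marked.

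**2. Three candidate analyses, class ignored.** The variance relative to the week-4 score is 1 for week-4 only, 2(1 − r) for change and 1 − r² for the adjusted comparison (ANCOVA). Required n per group for power 0.95 is 104 times that factor. Power is by noncentral t with 100 per group, on 198 df (197 for ANCOVA). CI half-width is t × √(2/100) × √factor.

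| Analysis | Quantity | r = 0.3 | r = 0.5 | r = 0.7 |
|---|---|---|---|---|
| Week-4 only | n per group | 104 | 104 | 104 |
| | power | 0.940 | 0.940 | 0.940 |
| | half-width (SD) | 0.28 | 0.28 | 0.28 |
| Change | n per group | 146 | 104 | 63 |
| | power | 0.845 | 0.940 | 0.995 |
| | half-width (SD) | 0.33 | 0.28 | 0.22 |
| ANCOVA | n per group | 95 | 78 | 54 |
| | power | 0.958 | 0.982 | 0.998 |
| | half-width (SD) | 0.27 | 0.24 | 0.20 |

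Adjustment cuts the variance of the week-4 comparison by r², that is 9%, 25% and 49%. One-sided, power is 0.970 for week-4 only and 0.980/0.992/0.9995 for ANCOVA. If only 87 per group are analyzed, two-sided power is 0.906 for week-4 only, 0.791/0.906/0.989 for change and 0.930/0.966/0.996 for ANCOVA.

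**3. A chance baseline gap.** If the arms differ by 0.3 SD before training, the week-4 estimate shifts by r × 0.3 = +0.09/+0.15/+0.21 SD. The change estimate shifts by (r − 1) × 0.3 = −0.21/−0.15/−0.09 SD. With 100/3 = 33.3 pupils per class, the gap has SD √(2[1 + 32.3 × ICC]/100): 0.141 at ICC 0 and 0.229 at ICC 0.05. The probability of a gap beyond 0.3 SD in either direction is then 3% and 19%.

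**4. Does the gain survive an analysis by class?** Compare 3 + 3 class means on 4 df, with 33 pupils per class and variance 2[1 + 32 × ICC](1 − r²)/99. Power:

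| ICC | unadjusted | r = 0.3 | r = 0.5 | r = 0.7 |
|---|---|---|---|---|
| 0.02 | 0.55 | 0.59 | 0.67 | 0.82 |
| 0.05 | 0.39 | 0.42 | 0.48 | 0.63 |
| 0.10 | 0.26 | 0.28 | 0.33 | 0.45 |

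At ICC 0.05 the CI half-width falls from 0.64 SD to 0.61/0.55/0.45 SD. Simulation (8,000 trials per setting) of the class-means method set out in the fix agrees: power 0.409/0.477/0.640 at ICC 0.05, and type I error 0.045 to 0.054 over ICC 0 to 0.10. If class means do not correlate over time (class-level r = 0, pupil r = 0.5, ICC 0.05), the gain vanishes: 0.37 adjusted against 0.38 unadjusted.

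**5. What adjustment does not do.** In the same simulations, tests that ignore class at ICC 0.05 have type I error 0.220 to 0.231 on the week-4 score and 0.218 to 0.223 with ANCOVA.

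**The case against.** The strongest reply is that adjustment is an efficiency preference. If the draw allocates classes to arms at random, a baseline gap is sampling error, and an unadjusted test on the week-4 score is a legitimate comparison, class aside. At r = 0.3 to 0.5 ANCOVA adds only 2 to 4 points of power at 100 per group; a larger gain needs r near 0.7, and no document gives r. This stands, and it limits the weight of the point. It does not answer the second half: the score to be tested is not stated, and the required n under the two readings agrees only at r = 0.5.

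Three narrower replies also have merit. A change-score test would use the pre-test, so the charge of wasted data applies only to a week-4-only test. The control pre-test is inferred from Study Design, and Sample itself expects incomplete data and absenteeism, so not every pupil will have both scores. Finally, the low class-level powers come from clustering, not from lack of adjustment. None of these supplies the missing specification.

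**Conclusion.** The concern holds. The plan specifies no between-arm comparison adjusted for the pre-test and does not say which score the independent t-test uses; no other section fills the gap.

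Ignoring class, adjustment reduces the variance of a week-4 comparison by 9% to 49% for r from 0.3 to 0.7. The unstated choice between week-4 score and change moves the required n per group from 104 to anywhere between 63 and 146. At class level with ICC 0.05, power rises from 0.39 to between 0.42 and 0.63. All of this rests on assumed r and ICC. The benefit is small near r = 0.3 and absent if class means do not correlate over time.

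This is lost precision and an undetermined primary test, not a demonstrated bias. It does not make the stated 87 per group wrong. The change should be made because it improves the analysis at almost no cost.

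**What to change.** In Statistical Analysis, name one primary analysis: the between-arm difference in week-4 total score, adjusted for each pupil's own pre-test total score, reported with a 95% CI. Carry it out within whatever class-respecting analysis is adopted. One workable form is to adjust each pupil's week-4 score using the pooled within-class slope on the pre-test, then compare the 3 + 3 class means with a t-test on 4 df. Label the dependent t-tests descriptive. It would help to state in the Control Arm section that controls complete the scale at the same two times, and to say how pupils missing one score are handled.

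For the adjustment itself the cost is wording only, since both measurements are already planned. The low power of a 4-df comparison is a consequence of having three classes per arm and must be dealt with as a separate matter.

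### Whole classes are drawn to the arms, three against three, but the only between-arm test treats pupils as independent, so its p-value is too small for any positive within-class correlation

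*Combined protocol and SAP*

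**What the plan says.** The unit drawn is the class. Under Sample: "3 branches will be selected for the experimental group and 3 branches for the control group. Branches will be determined by drawing". The Intervention arm section confirms that "the groups will be designated as class branches", and the Control Arm section repeats the draw: "3 branches for the control group. Branches will be determined by drawing". The four weekly training sessions go to the students of the drawn branches.

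The sample size is counted in pupils. With "effect size 0.50, and power 0.95", "the minimum number of participants was 87 in the experimental group and 87 in the control group". This is raised to 100 per group for possible non-normality, incomplete or erroneous data, and absence. Clustering is not among the reasons.

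The whole analysis plan is percentages, means and two tests ("t-test for independent samples and t-test for dependent samples will be used"), with significance at p < 0.05. The documents contain no class effect, class-level summary, ICC or design effect.

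**The concern.** The dependent-samples t-test works within one group, so the independent-samples t-test is by inference the primary comparison. It judges the arm difference against the spread between pupils. In this design the difference also carries the spread between classes, of which there are only three per arm.

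Some within-class similarity is plausible on the protocol's own account. The classes come from two grades and no stratification by grade is described. The introduction counts peer influences and norms among the targets of injury prevention. Pupils in a trained class also share their sessions.

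If that similarity is ignored, chance differences between classes can be read as an effect of the education. This is the only between-arm test of the only stated hypothesis. A confidence interval from the same test would be too narrow, and the planned power would describe a trial that randomised individual pupils.

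**Working it through.** **Inputs.** From Sample: three classes per arm, 100 pupils per arm, effect size 0.50, alpha 0.05, power 0.95, minimum 87 per arm. Derived: class size m = 100/3 = 33.3. Assumed: ICC from 0 to 0.10, for a single unadjusted score, because the documents give none.

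**1. The plan's own figure.** For independent pupils, n per arm = 2(z_alpha + z_power)² / d².

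- One-sided: 2(1.645 + 1.645)² / 0.25 = 86.6, so 87. This reproduces the plan (an exact t calculation gives 88).
- Two-sided: 2(1.960 + 1.645)² / 0.25 = 104.0, so 104 (exact t gives 105).

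The 87 therefore matches a one-sided test of independent pupils, with a design effect of 1. The plan does not state sidedness, and its hypothesis is non-directional. All results below are two-sided unless marked.

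**2. Design effect.** DE = 1 + (m − 1) × ICC. At ICC 0.05, DE = 1 + 32.3 × 0.05 = 2.62. The true standard error is then about √2.62 = 1.62 times the one the t-test assumes, and 100 pupils per arm carry the information of about 100/2.62 = 38.

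**3. Type I error of the planned test.** As an approximation, error = 2[1 − Φ(1.96/√DE)]. At ICC 0.05 this is 2[1 − Φ(1.21)] = 0.226. Simulation with normal class effects (variance ICC), normal residuals (variance 1 − ICC), classes of 33, 33 and 34 per arm and 200,000 trials per ICC gives 0.228.

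**4. A valid comparison on six class means (4 df).** The variance of the difference is (2/3)[ICC + (1 − ICC)/33.3]. At ICC 0.05 this is (2/3)(0.05 + 0.0285) = 0.0523, so the standard error is 0.229 and the noncentrality is 0.50/0.229 = 2.19. The two-sided critical value on 4 df is 2.78, and power is 0.387. The simulated type I error of this test is 0.050 to 0.051 at every ICC.

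| ICC (assumed) | DE | SE understated by | Type I error, planned t-test | Power, class-mean t-test, d = 0.50 | Classes per arm for 0.95 power |
|---|---|---|---|---|---|
| 0 | 1.00 | 1.00 | 0.050 | 0.753 | 5 |
| 0.005 | 1.16 | 1.08 | 0.070 | 0.693 | 5 |
| 0.01 | 1.32 | 1.15 | 0.090 | 0.639 | 6 |
| 0.02 | 1.65 | 1.28 | 0.128 | 0.551 | 7 |
| 0.05 | 2.62 | 1.62 | 0.228 | 0.387 | 10 |
| 0.10 | 4.23 | 2.06 | 0.348 | 0.264 | 15 |

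The last column keeps about 33 pupils per class, with no baseline adjustment and 2k − 2 df for k classes per arm. Repeat simulations agreed to within about 0.002 on type I error.

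**5. Limit of the design.** An exact permutation test of three classes against three has 20 possible allocations. Its smallest two-sided p-value is 2/20 = 0.10, so it can never reach p < 0.05.

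**The case against.** The strongest reply is that the ICC is unknown, so only the direction of the error is established. A change score or baseline-adjusted score may also have a different ICC from a raw score. That stands, and no single row of the table should be taken as the expected value. The direction holds, though: with about 33 pupils per class, the design effect exceeds 1 for any positive ICC, including the ICC of change.

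Second, the power contrast mixes sidedness. The class-mean figures are two-sided, while 87 per arm matches only a one-sided test. Compared like for like at 100 per arm and two-sided, the pupil-level test with no clustering has power 0.94, against 0.64 (ICC 0.01) and 0.39 (ICC 0.05) for class means. One-sided, the figures are 0.97 against 0.81 and 0.56. One-sided class-mean power is 0.89 even at ICC 0, so it misses 0.95 either way.

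Third, part of the loss is the price of having 4 df. At ICC 0 the class-mean test already falls from 0.94 to 0.75. This is true, and it is a consequence of having only six classes.

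Fourth, the analysis section does not name the unit of analysis, so a pupil-level test is an inference. It is a strong one, because the sample size counts pupils and no class summary is planned. The quasi-experimental label does not change the matter: class is still the unit drawn and trained.

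**Conclusion.** The concern holds. Followed as written, the plan gives an anti-conservative test of its only hypothesis unless the within-class correlation is zero or negative. Over the assumed ICC range of 0.005 to 0.10, a nominal 5% test has a true error of about 7% to 35%. The stated power of 0.95 has no basis for three classes against three. These sizes rest on the assumed ICCs, normally distributed class effects, near-equal classes of about 33 and unadjusted scores. This must be corrected before the data are analysed.

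**What to change.** In Statistical Analysis, replace the independent-samples t-test as the primary comparison with one of the following, chosen before the data are seen:

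1. A linear mixed model for post-test score with arm, baseline score and a random class intercept, using Kenward-Roger or Satterthwaite degrees of freedom. An unadjusted, balanced approximation puts its type I error at about 3% to 5.4%; the adjusted version was not checked.
2. A t-test on three against three baseline-adjusted class means. Adjust at pupil level first and then average by class, which keeps 4 df. Using the class-mean baseline as a covariate would leave 3 df.

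Keep the pupil-level t-test as descriptive only. Record a class identifier on every form. Report the estimated ICC as a rough guide: with six classes, the between-class variance was estimated as zero in about 44% of simulated trials at a true ICC of 0.01, and in 17% at 0.05.

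In Sample, state whether the test is one- or two-sided, restate power for three classes per arm over a stated ICC range, and either add classes or say plainly that the lower power is accepted.

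**Cost.** The analysis change is one rewritten paragraph and one extra field per form, with no additional pupils or visits. It does not restore power, although baseline adjustment may recover some. Regaining 0.95 would take about 5 to 15 classes per arm over ICC 0.005 to 0.10, unadjusted, which is a real design cost.

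### The analysis plan lists within-arm and between-arm t-tests under one 0.05 threshold and does not say which one decides the hypothesis

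*Combined protocol and SAP*

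**What the plan says.** The Statistical Analysis section is two sentences long. The first names percentages, the arithmetic mean and two tests: "t-test for independent samples and t-test for dependent samples will be used". The second gives a single threshold: "Significance level will be taken as" p < 0.05. It does not say which scores each test compares, which test is decisive, or whether the within-arm tests are descriptive.

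No other section supplies the decision rule:

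- The Hypothesis section says that the education "affects the safety precautionary behavior of students for school accidents". It names no comparator and no time point.
- Primary Outcomes names the behavior outcome without a contrast.
- Study Design states: "It has a pretest-posttest design with a control group".
- The Sample section takes its effect size from "The behavior score averages and standard deviations of the two groups in a previous study", and reports that "the minimum number of participants was 87 in the experimental group and 87 in the control group".

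The last two items point towards a between-arm comparison. Neither is linked to how the hypothesis will be judged.

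**The concern.** The dependent t-test asks whether one arm's mean moved between pretest and posttest. It makes no use of the control group, whose purpose is to remove movement unrelated to the training. Completing the same scale a second time, or four more weeks of school, could shift scores in both arms. If so, a significant change in the trained arm would not show that the training worked.

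Setting a significant trained-arm change beside a non-significant control-arm change does not repair this. It compares two p-values, and the difference between the two changes is never tested.

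As written, the plan would let either result be presented as support for the hypothesis without departing from it, even if the between-arm difference were null. What is at stake is the error rate of the trial's only hypothesis on its only primary outcome.

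**Working it through.** **Step 1. What the sample size was built for.** Inputs from the Sample section: "significance level 0.05 for type 1 error, effect size 0.50, and power 0.95". For two independent means, n per arm = 2(z₁₋α + z₁₋β)² / d².

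- One-sided: 2(1.645 + 1.645)² / 0.25 = 86.6, so 87. The exact noncentral-t answer is 88.
- Two-sided: 2(1.960 + 1.645)² / 0.25 = 104.0, so 104. The exact answer is 105.
- A dependent t-test with a standardized change of 0.50 would need only 45 pupils (one-sided) or 54 (two-sided) in a single group.

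The stated 87 per arm is therefore reproduced as a two-group, one-sided calculation. It does not match a paired one. Sidedness is a separate matter and does not affect this point.

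**Step 2. Inputs for the error rates.** From the documents: "the research will be conducted with 100 participants in each group", and the 0.05 threshold, taken here as two-sided because the plan does not say. Assumed, because the documents give no figure: pre-post correlation r from 0.5 to 0.7; a common drift δ in both arms from 0 to 0.30 SD of the score; equal SDs at both times; pupils independent (class branches ignored). The true training effect is set to zero.

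**Step 3. Trained-arm dependent t-test.** The standardized change is dz = δ / √(2(1 − r)) and the noncentrality is dz·√100. The critical value is 1.984 on 99 df. Example: δ = 0.20 and r = 0.6 give dz = 0.20/√0.8 = 0.2236, noncentrality 2.236, and a 60.0% chance of significance.

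| Common drift (SD) | r = 0.5 | r = 0.6 | r = 0.7 |
|---|---|---|---|
| 0 | 5.0% | 5.0% | 5.0% |
| 0.05 | 7.9% | 8.6% | 9.8% |
| 0.10 | 16.8% | 19.8% | 24.8% |
| 0.20 | 50.8% | 60.0% | 72.5% |
| 0.30 | 84.4% | 91.3% | 97.0% |

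**Step 4. Trained arm significant upward, control arm not significant.** This is P(trained significant upward) × P(control not significant). Example: δ = 0.20 and r = 0.6 give 0.600 × (1 − 0.600) = 0.240.

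| Common drift (SD) | r = 0.5 | r = 0.6 | r = 0.7 |
|---|---|---|---|
| 0 | 2.4% | 2.4% | 2.4% |
| 0.10 | 13.8% | 15.8% | 18.6% |
| 0.20 | 25.0% | 24.0% | 20.0% |
| 0.30 | 13.2% | 7.9% | 2.9% |

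The rate rises to about 25% and then falls, because with larger drift the control arm becomes significant too.

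**Step 5. Between-arm test, and accepting either test.** In 20,000 simulated trials per setting, at r = 0.5 and 0.7, an independent t-test on posttest or on change rejected in 4.6% to 5.2% of trials at every drift from 0 to 0.30 SD. Counting success when either the trained-arm paired test or the between-arm posttest comparison is significant gave 9.3% to 9.6% at zero drift. If the two tests were independent, the figure would be 1 − 0.95² = 9.75%. At 0.20 SD of drift the either-test rate was 53.1% to 74.0%.

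**The case against.** The strongest reply is that the between-arm test is plainly the intended one. There is a control group, the effect size comes from two groups, and Step 1 shows that 87 per arm fits a two-group comparison. This stands as evidence of intent. A reader might infer from the shared list and threshold that the plan ranks the two tests equally, or that the sponsor means to claim success from a within-arm result. The documents support neither reading. The list also contains percentages and means, and no section says that a within-arm change will count as proof. What remains is an omission: the deciding test is not named.

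A second reply is that drift is speculative. That also stands. The documents give no drift figure, no retest data and no pre-post correlation, and over four weeks drift could be close to zero. The tables therefore start at zero, and no single cell is a prediction. The omission does not depend on drift, because accepting either test nearly doubles the error even without it.

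A third reply is that a dependent t-test is a legitimate procedure. It is: it keeps its 5% rate for its own null hypothesis, no change in that arm. It misleads only when read as a test of the training effect, and labelling it as descriptive would meet the concern.

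**Conclusion.** The point holds as an ambiguity that should be closed before analysis. The plan does not say which test decides the hypothesis, and it leaves room for two readings that do not test the training effect.

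The omission itself is certain from the text. Its size is conditional. With no training effect and the assumptions in Step 2, the trained-arm paired test is significant in 5% of trials at zero drift, rising to between 84.4% and 97.0% at 0.30 SD. The pattern of one arm significant and the other not runs from about 2% at zero drift to a peak near 25%, then back to between 2.9% and 13.2% at 0.30 SD. A single between-arm test stays near 5% throughout, but only while pupils are treated as independent. Whole class branches are allocated, three per arm, so an ordinary between-arm t-test is not assured that rate either.

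**What to change.** In the Statistical Analysis section, state that:

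1. The hypothesis is decided only by one between-arm contrast: total behavior score at the end of week 4, adjusted for the pretest score, reported as a mean difference with 95% CI and allowing for the six class branches.
2. Each arm's pre-post change is shown for description only.
3. No conclusion will rest on one arm changing significantly and the other not.

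This assumes that control pupils complete the scale at both times, as the Study Design section implies.

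The cost is wording. No further pupils or data are needed, and naming a between-arm test agrees with the basis of the 87 per arm. The sponsor gives up within-arm p-values as evidence of effect. Allowing for the branches can widen the interval, by an amount that cannot be stated because the documents give no within-class correlation.
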